7.6. Discontinuation or Withdrawal of a Subject

Patients are free to withdraw from the study at any time and for any reason without prejudice to their future medical care by their physician or at the institution. The Investigator may discontinue

PROTOCOL

Title: Safety and Efficacy of Encapsulated Allogeneic FVIII Cell Therapy in Haemophilia A
Study No. SIG-001-121

a subject's study participation at any time during the study. The Investigator may remove a patient from the study for medically indicated reasons, for non-compliance, or if, in the Investigator's opinion, it is not in the best interest of the patient to continue the study. When possible, the tests and evaluations listed for the last study visit should be carried out in the event of premature termination.

The primary reason for discontinuation or withdrawal of the subject from the study or study treatment should be recorded in the eCRF. The Investigator is responsible for ensuring all safety assessments and final follow up assessments, including follow up for unresolved AEs, are completed prior to subject discontinuation.

If a patient fails to return for scheduled visits, a documented effort must be made to determine the reason. If the patient cannot be reached by telephone, a certified letter should be mailed. This information should be recorded in the study records. For subjects withdrawn or lost to follow-up, the Investigator may continue to collect available long-term follow-up information where possible and permissible by local IRB/IEC policy, except where the subject has withdrawn consent for further information to be collected. The Sponsor must be notified of all patient withdrawals as soon as possible.

7.7. Discontinuation of the Study or Investigative Site

The Sponsor has the right to terminate the study at any time for clinical or administrative reasons and/or to discontinue participation of an individual Investigator or site for clinical or administrative reasons, including, but not limited to, poor enrolment or noncompliance with procedures of the protocol or GCP.

If the Sponsor suspends or terminates the trial or part of the trial, the Investigators and IEC/IRB will be promptly notified in writing with the reason for suspension/termination as per applicable regulatory requirements.

8. CLINICAL TRIAL INVESTIGATIONAL PRODUCT MANAGEMENT

This section contains information regarding all investigational product and materials provided directly by the Sponsor, and/or sourced by other means, that are required by the study protocol, including important sections describing the handling and management of the clinical trial investigational product (SIG-001).

8.1. Investigational Product

In this protocol, the term study drug or Investigational Product (IP) refers to:

- SIG-001 spheres in buffer, provided in trays (see the *SIG-001 Investigator's Brochure* for complete description)

No placebo or other active medicinal product is supplied. SIG-001 must be prepared, handled, and administered by qualified site staff who have been trained to the procedures for IP

PROTOCOL

Title: Safety and Efficacy of Encapsulated Allogeneic FVIII Cell Therapy in Haemophilia A
Study No. SIG-001-121

preparation outlined in the *Laparoscopic Procedure Manual*. SIG-001 is to be dispensed only to patients enrolled in this study.

SIG-001 must be administered in accordance with the *Laparoscopic Procedure Manual* by a surgeon who has received study-specific training and must not be used after the expiry date and time.

8.1.1. Sponsor-Supplied Investigational Product

SIG-001 is supplied as a dose of spheres by volume suspended in buffer. SIG-001 is manufactured by Sigilon Therapeutics, Inc. via a GMP-compliant Contract Manufacturing Organizations (CMO).

SIG-001 is supplied in polyethylene terephthalate (PETG) trays with foil lids. Each SIG-001 tray is labelled in accordance with applicable laws and regulations (see the *Pharmacy Manual* for details on packaging and labelling).

8.1.2. Sponsor-Supplied Kits and Delivery Equipment

Study-specific clinical kits will be provided to sites prior to start of enrolment. These kits will contain supplies that are required for IP preparation and administration (e.g. a sterile drape, sterile tip syringes, administration buffer, catheter for intraperitoneal administration, 8mm disposable laparoscopic trocars).

These kits will be maintained in stock at clinical sites. Final content of the kit(s) and detailed instructions for preparation and use are defined in the *Laparoscopic Procedure Manual* and the *Pharmacy Manual*.

8.1.3. Storage

SIG-001 must be stored at 15°C - 25°C (59°F - 77°F). Brief temperature excursions during transit and/or storage may be acceptable. Any discrepancies or deviations from the above referenced temperature conditions must be reported to the Sponsor and resolved prior to IP administration. SIG-001 will be shipped in a qualified shipping container with a temperature monitor. Upon receipt of the product at the clinical site, the product batch number will be recorded, and the temperature monitor will be checked to ensure the product remained within the defined temperature conditions during transit.

Investigational product must be kept in a location with access limited to study staff until it is transferred to the surgical suite for preparation by the surgeon. Investigational product must be stored separate from normal hospital/practice inventory and be clearly identified from other investigational supplies or products. SIG-001 must be administered in accordance with the *Laparoscopic Procedure Manual* and must not be used after the expiry/use-by date and time. While all SIG-001 is expected to be administered to patients, SIG-001 not administered to a patient must be returned to the Sponsor or designee or destroyed per the site's standard procedures.

Investigational product must be stored under the conditions specified on the label, and must remain in the original container until used or destroyed. Sites should use caution to avoid temperature fluctuations or exposure to mechanical agitation, dropping, shaking, or stirring of the product.

The SIG-001 protective plastic pouch and foil lid should only be removed in the operating room,

Version: 5.0

Page 38 of 72

04 March 2021

CONFIDENTIAL

PROTOCOL

Title: Safety and Efficacy of Encapsulated Allogeneic FVIII Cell Therapy in Haemophilia A
Study No. SIG-001-121

immediately prior to preparation for surgery.

Additional details on storage, handling, and administration are included in the *Pharmacy Manual* and *Laparoscopic Procedure Manual*.

8.2. Product Assignment and Dispensing Procedures

8.2.1. Randomization and Blinding

No randomization or blinding is employed in this trial.

8.2.2. Accountability and Disposition Procedures

Sites must maintain an accurate study product Accountability Log throughout the study. While all SIG-001 is expected to be administered to patients, SIG-001 not administered to patients must be returned to the Sponsor or designee or destroyed per the site's standard procedures.

The Investigator or designee must ensure that the sponsor-supplied product and kits are used in accordance with the protocol and are dispensed only to subjects enrolled in the study. To document appropriate use of sponsor-supplied product and kits, the Investigator or designee must maintain records of all sponsor-supplied products and kits to the site, site inventory, dispensation and use by each subject, and return to the Sponsor or designee.

Proper product accountability includes, but is not limited to:

- Continuously monitoring expiration date/use-by date and time.
- Verifying that actual inventory matches documented inventory.
- Verifying that all containers used are accurately documented on the log.
- Verifying that required fields are completed accurately and legibly.

If any dispensing errors or discrepancies are discovered, the Sponsor must be notified immediately.

In the event of expiry date extension of supplies already at the study site, sponsor-supplied products may be relabelled with the new expiry date at that site. In such cases, Sigilon Therapeutics or its designee will prepare additional labels and all necessary documentation for completion of the procedure at the sites.

9. STUDY PLAN

9.1. Screening and Enrolment

9.1.1. Screening of Subjects

Following completion of the consenting process, patients will undergo screening assessments as described in the Schedule of Assessments (Table 2 Schedule of Assessments). Once eligibility is verified, the Investigator or site staff will work with the patient to schedule the SIG-001 placement procedure. If the laparoscopic procedure is scheduled outside of the original screening window, the patient will return to the clinic for Screening Visit 2 to repeat select screening assessments. The reason for completing Screening Visit 2 should be clearly documented. Patients must undergo SIG-001 placement within 90 days of consent.

PROTOCOL

Title: Safety and Efficacy of Encapsulated Allogeneic FVIII Cell Therapy in Haemophilia A
Study No. SIG-001-121

All screening evaluations must be completed and reviewed to confirm that potential subjects meet all eligibility criteria. Screening assessments may be completed over several screening visits. The Investigator will maintain a screening log to record details of all subjects screened and to confirm eligibility or record reasons for screening failure, as applicable.

9.1.2. Screen Failures

Screen failures are defined as patients who consent to participate in the clinical study but who do not subsequently receive the study product. A minimal amount of information is required to ensure transparent reporting of screen failure subjects in compliance with the Consolidated Standards of Reporting Trials requirements and to respond to queries from regulatory authorities. Minimal information includes reporting of demographics, screen failure details, eligibility criteria, and any AE/SAE. Screen failure data will be recorded within the electronic Case Report Form (eCRF).

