products; adequate FVIII levels will be ensured during hospital and home dosing. As needed, patients may be discharged with peripherally inserted central catheter (PICC) lines. Per the Investigator's discretion, patients may remain longer in the hospital for observation during FVIII administration.

Patients will be withdrawn from FVIII therapy after the Week 1 post-op visit at the Investigator's discretion. Throughout the study, all patients will be allowed access to on-demand FVIII to treat bleeding episodes, as perioperative management for surgery or other medical procedures, or as preventative treatment prior to vigorous physical activity.

Throughout the study, FVIII levels will be assessed at regular intervals. Per the Investigator's discretion, exogenous FVIII use will be washed out for a minimum of 96 hours (4 days for standard half-life FVIII products) and at least 168 hours (7 days for prolonged half-life rFVIII products) to ensure that only FVIII secreted by SIG-001 is measured.

ANALYTICAL METHODS:

Sample Size justification:

The sample size for this Phase 1/2 study is not based on statistical considerations.

Study Populations:

Efficacy Analysis Set includes all patients who received the study product and had at least one post-baseline efficacy assessment.

Safety Analysis Set includes all patients who received study product.

General Statistical Methods:

No formal hypothesis testing is planned in the study. Instead, results will be analysed using descriptive statistics. Data will be summarized by cohort and overall, where appropriate.

Absolute values and changes from baseline (Δ baseline) will be descriptively summarized for vital signs, laboratory data and FVIII inhibitor titres (Nijmegen Bethesda assay).

Data on FVIII activity, annualized bleeding and FVIII usage, as well as Haem-A-QoL, EQ-5D-5L questionnaires, joint health, and physical activity will be summarized descriptively and provided in subject listings. Questionnaires will be scored according to the recommendations from the questionnaire authors. Haem-A-QoL, EQ-5D-5L and HJHS scale scores and sub-scale scores and changes from baseline will be calculated at planned timepoints for each dose cohort and overall.

Full methods of analysis will be presented in the *Statistical Analysis Plan*.

Preliminary Efficacy Analysis:

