6.6.2. Dose Limiting Toxicities and Cohort and Study Stopping Rules

DLTs are defined as the AEs and SAEs listed below. DLTs will be recorded from first patient administration until 8 weeks after last patient administration of SIG-001. All AEs/SAEs will be graded and reported as per Section 12 Safety and Adverse Events.

Any occurrence of the DLTs listed below will trigger an ad hoc evaluation by the SRC and further dosing or dose escalation in the trial will be halted.

- Any death
- Any SAE that is considered possibly or probably related to SIG-001, which is deemed to pose unacceptable risk to study participants
- Any surgical SAE that is considered possibly or probably related to the anaesthesia or laparoscopic procedure, deemed to pose an unacceptable risk to study participants, and occurs in more than 2 patients at any dose level
- Any Grade III-IV toxicity assessed as possibly or probably related to the study product. Examples include, but are not limited to:
 - Inhibitor development with persistent titres > 0.6 NBU/mL
 - Persistent abdominal pain
 - Persistently abnormal laboratory values, such as:
 - Alanine aminotransferase (ALT) elevations $> 5 \times$ upper limit of normal (ULN) in the absence of a concomitant bilirubin increase

PROTOCOL

Title: Safety and Efficacy of Encapsulated Allogeneic FVIII Cell Therapy in Haemophilia A
Study No. SIG-001-121

- ALT elevations $> 3 \times \text{ULN}$ in the presence of a total bilirubin increase $> 2 \times \text{ULN}$ or an international normalized ratio (INR) > 1.5 without findings of cholestasis or other alternate aetiology to explain the elevations
- ALT elevations $> 3 \times \text{ULN}$ with the appearance of fatigue, nausea, vomiting, right upper quadrant pain or tenderness, fever, rash and/or eosinophilia ($> 5\%$)
- Any thrombotic event
- Any peritonitis
- Abdominal adhesions/fibrosis
- Supratherapeutic levels of FVIII activity (above 150 IU/dL, or $> 150\%$ activity)
- An overall pattern of clinically significant changes in any safety parameter, considered to be potentially related to the study product that represents a safety concern.

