9.1.3. Informed Consent Procedure

Informed consent must be obtained prior to subject enrolment in the study (as described in Section 14.1.3) and before any protocol-directed procedures are initiated. A unique subject identification number (subject ID = site number + subject number) will be assigned to each subject at the time that informed consent is obtained; this subject number will be used throughout the study.

Individuals who do not meet the eligibility criteria for participation in this study (i.e., screen failure) may be rescreened once. Rescreened subjects will be assigned a new screening number that is different from the number assigned at the initial screening.

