9.2.3. SIG-001 Procedure

These procedures should be carried out in the sterile field by trained study staff as described in the *Laparoscopic Procedure Manual*.

SIG-001 must be administered by a study surgeon who has been trained to the procedures for SIG-001 administration outlined in the *Laparoscopic Procedure Manual*. SIG-001 is placed into the greater sac of the peritoneal space via laparoscopy conducted under general anaesthesia. Each site will use their standard, clinically used laparoscopic methods and instrumentation to complete the surgery, supplemented with equipment, reagents, and IP provided by the Sponsor, including an 8mm trocar and a 24F catheter. Once in the peritoneal space, the catheter is inserted through a trocar, and syringes containing SIG-001 spheres and buffer at approximately 1:2 volume ratio are attached firmly to the catheter and the contents slowly expelled, including air volume. Once all syringes containing SIG-001 are administered, a syringe containing buffer alone will be administered to expel any remaining spheres from the catheter. Complete details regarding SIG-001 administration are provided in the *Laparoscopic Procedure Manual*.

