9.2.4. Post-Procedure Activities

Following SIG-001 administration, patients will continue to receive FVIII to maintain trough levels $\geq 60\%$ for the first 48 hours after surgery. Patients may be discharged from the hospital on Day 3 or later per the Investigator's discretion.

FVIII dosing will be continued at home until the 1-week visit, to maintain minimal haemostatic trough levels of $\geq 30\%$ of FVIII activity. This post-procedure FVIII treatment regimen may involve twice daily dosing for standard half-life products or once daily dosing for extended half-life products. Patients may be discharged with a PICC line as needed. Per the Investigator's discretion, patients may remain in the hospital for longer observation during FVIII administration.

Patients will be withdrawn from FVIII therapy after the Week 1 (Day 7) visit, per the Investigator's discretion. If patients are not withdrawn from FVIII therapy at Week 1, the reason for continuing FVIII will be recorded.

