13.6. Safety Analyses

All patients who received study product will be included in the Safety Analysis Set.

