13.6.1. Adverse Events

Treatment-emergent AEs will be summarized for each dose cohort by severity and relationship to study product and relationship to the study procedure. SAEs will be presented for each dose cohort by relationship to study product and relationship to the study procedure. Summary tables will present incidence estimates and individual event rates by system organ class as well as within each system organ class. Severity will be summarized by CTCAE v5.0 grading. Patients experiencing an event more than once with varying severity will be counted only once, in the maximum grade within each system organ class and preferred term. For incidence of relationship to study product and study procedures, patients will be counted only once, in the category of the strongest relationship within each system organ class and preferred term.

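### Procedure-related adverse events are to be tabulated only in patients who received SIG-001, so a patient whose anaesthesia or laparoscopy was started but who got no spheres drops out of the planned safety tables

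*Protocol*

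**What the plan says.** Two definitions decide who is counted.

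- **Screen failure, Section 9.1.2:** "Screen failures are defined as patients who consent to participate in the clinical study but who do not subsequently receive the study product." No point in the patient's course ends this status.
- **Screen failure, Section 9.1.3:** a narrower use tied to eligibility: "Individuals who do not meet the eligibility criteria for participation in this study (i.e., screen failure) may be rescreened once."
- **Safety Analysis Set, synopsis:** "Safety Analysis Set includes all patients who received study product." Section 13.6 agrees: "All patients who received study product will be included in the Safety Analysis Set."

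The procedure is an exposure of its own, and it comes first. Section 9.2.3: "SIG-001 is placed into the greater sac of the peritoneal space via laparoscopy conducted under general anaesthesia." Section 12.1.7 has each adverse event rated separately for its relation to the product and to the laparoscopy. Section 13.6.1 carries this into the tables: "Treatment-emergent AEs will be summarized for each dose cohort by severity and relationship to study product and relationship to the study procedure." SAEs are handled in the same way.

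Section 6.6.2 includes a dose-limiting toxicity (DLT) criterion for surgical SAEs related to anaesthesia or laparoscopy. On timing it says: "DLTs will be recorded from first patient administration until 8 weeks after last patient administration of SIG-001."

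No section covers surgery that begins and ends without placement.

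**The concern.** The primary objective is the safety of SIG-001 given by laparoscopy, and Section 4.5 acknowledges that patients would not have this operation under standard care. Procedural safety is therefore part of what the trial sets out to describe.

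A patient can undergo anaesthesia and trocar entry and then receive nothing, for example because of a bleed, an anaesthetic event, unexpected adhesions or a product problem in theatre. Under the definitions above, that patient is a screen failure and lies outside the Safety Analysis Set. Where a complication stopped the placement, the event that makes the procedure look risky is also what removes the patient. Event and patient leave the numerator and denominator together, so the tabulated rate is too low. Cohorts have three to six patients, so one such case changes the impression a table gives.

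**Working it through.** **Inputs.** The maximum sample size is 18 (Section 13.2), which agrees with 3 cohorts × (3 + 3) = 18. The study is descriptive (Section 13.1), so there is no power or error rate to reproduce. The documents give no abandonment rate; every rate and event count below is an assumption.

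**Step 1: follow the definitions.** Take a patient in whom anaesthesia is started and no spheres are placed.

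| Question | Answer as written |
|---|---|
| Screen failure under 9.1.2? | Yes, no product received |
| Screen failure under 9.1.3? | Not clearly; eligibility may have been met |
| In the Safety Analysis Set (synopsis, 13.6)? | No, under either meaning of screen failure |
| AEs and SAEs recorded? | Yes (9.1.2, 12.2.1) |
| SAEs seen by the SRC? | Yes (11.1) |

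The exclusion from the tables rests on the analysis set alone and does not depend on which meaning of screen failure is used.

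**Step 2: effect on a reported rate.** Assume one abandoned procedure with a procedure-related SAE and no such SAE in treated patients. The abandoned patient is added to the treated count because Section 7.2 counts patients enrolled to receive SIG-001. Intervals are exact (Clopper-Pearson) 95%.

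| Setting | As planned | All procedures started |
|---|---|---|
| Initial cohort | 0/3 (0 to 70.8%) | 1/4 = 25.0% (0.6 to 80.6%) |
| Expanded cohort | 0/6 (0 to 45.9%) | 1/7 = 14.3% (0.4 to 57.9%) |
| Whole study | 0/18 (0 to 18.5%) | 1/19 = 5.3% (0.1 to 26.0%) |
| Whole study, two such patients | 0/18 (0 to 18.5%) | 2/20 = 10.0% (1.2 to 31.7%) |

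**Step 3: direction.** The bias is downward only when a complication causes the abandonment. If the cause is a product problem with no adverse event, and one treated patient has an event, the planned figure is 1/18 = 5.6% and the wider one 1/19 = 5.3%. The planned table then shows the slightly higher rate.

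**Step 4: how likely is any such patient?** With abandonment probability q per attempt, the chance of at least one in 18 attempts is 1 − (1 − q)^18.

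| Assumed q | Chance of at least one |
|---|---|
| 1% | 16.5% |
| 2% | 30.5% |
| 5% | 60.3% |
| 10% | 85.0% |

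These are chances of any abandonment. The case that lowers the reported rate needs an abandonment with a procedure-related event, which is less likely.

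**The case against.** A safety set of treated patients is conventional and fits an objective about SIG-001 as administered. All summaries are descriptive, and a single serious surgical event would be known to everyone who matters. This stands as a reason to rate the point low. It does not justify tabulating procedure-related events against a denominator that leaves out some of the procedures.

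Several stronger readings are tempting, and the documents do not support them.

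- **That such events are lost.** Sections 9.1.2 and 12.2.1 have events in screen failures recorded, Section 12 has AEs followed until resolved or stable, Section 12.2.2 does the same for SAEs, and Section 11.1 has the SRC review all SAEs.
- **That a surgical SAE in such a patient falls outside the DLT rule.** The recording window in 6.6.2 runs for the whole study, not per patient, so after the first dosing an abandoned procedure lies inside it. The surgical-SAE criterion does not require receipt of spheres, and any death is listed without a dosing condition. Two things remain unclear: an event before the first administration in the study, and how a patient without a dose is placed in a count made by dose level.
- **That the patient belongs to no cohort.** Sections 6.4 and 13.3 attach cohort to enrolment, not to receipt.
- **That post-operative care is not covered.** Section 9.2.4 does open narrowly: "Following SIG-001 administration, patients will continue to receive FVIII to maintain trough levels." But that section's title and the matching synopsis paragraph speak of the period after the procedure. Unscheduled visits (9.4) and assessments on discontinuation (7.6) are also provided. This is a wording mismatch.
- **That only fully successful placements count.** A partly dosed patient has received study product and stays in the set.
- **That the protocol foresees abandoned surgery.** Sections 8.1.3 and 8.2.2 mention product not administered, but as accountability text that expects all product to be given.

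**Conclusion.** The point holds in a limited form. As written, the summaries by relationship to the procedure leave out any patient whose procedure was started but who received no spheres. The reported procedure-related rate is then too low whenever a procedural complication caused the abandonment. One such patient would be the difference between 0/3 and 1/4 in an initial cohort, or between 0/18 and 1/19 overall. Those counts are assumed, and with no abandonment rate in the documents the frequency cannot be judged. A reader might infer a general downward bias, or a gap in safety oversight; neither follows, since the direction depends on the cause and the events still reach the databases and, if serious, the SRC. Because the protocol itself fixes both the analysis set and the screen-failure definition, this is not a detail awaiting the SAP. It is a change to consider, not one on which the trial's validity depends.

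**What to change.** 1. **Section 13.6 and synopsis:** summarise AEs and SAEs by relationship to the procedure in all patients in whom anaesthesia for the SIG-001 procedure was started, by intended dose cohort. Keep the existing treated-patient set for product-related summaries.
2. **Sections 9.1.2 and 9.1.3:** end screen-failure status at the start of anaesthesia, and make the two uses of the term agree.
3. **Section 6.6.2:** state whether a surgical SAE in a patient who received no spheres, including one before the first administration in the study, counts under the existing surgical-SAE criterion, and at which dose level.
4. **Section 9.2.4 and synopsis:** reconcile the two descriptions of when the post-operative text applies. No new clinical rule or visit schedule is proposed here.

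The cost is a few sentences and one extra denominator in the safety tables. Procedure-related rates may look slightly less favourable. Product-related analyses are unchanged.
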